# 5.3.2.1.2. Data Included

The main analysis of the primary endpoint will be conducted using the FAS. The FAS-N and modified FAS/FAS-N analysis sets will be used if there is a relevant difference from the FAS (>5% of participants in total).

FU Week 24 response status data from the selected population analysis set, after taking into account all the intercurrent events and applying the intercurrent event strategies in Section 5.3.2, will be included.

# 5.3.2.1.3. Assumptions

- Missing Data for HBsAg are Missing Not at Random (MNAR)
- The treatment effect is homogeneous across strata

# 5.3.2.1.4. Missing Data Handling Rule

Participants who withdraw from the study prior to FU Week 24 will be considered as non-responders.

If a participant remains in the study after experiencing a major protocol deviation (defined for the purpose of efficacy analyses and is an intercurrent event) and has missing FU Week 24 value, then the imputation to non-response will be applied. If the value for the endpoint at FU Week 24 is available, then such data will be used to determine their response status.

For the participants still in the study at FU Week 24 or for participants that have neither discontinued treatment early nor experienced any major protocol violations (defined for the purpose of efficacy analyses and is an intercurrent event), and HBsAg values missing at FU Week 24, then the primary method to handle missing data will be the missing as non-responder (MANR).

# 5.3.2.2. Sensitivity Estimators of the Main Estimand

Sensitivity analyses will be conducted by constructing three sensitivity estimators for the main estimand as defined in Section 5.3.2.

# 5.3.2.2.1. Sensitivity Estimator 1 of the Main Estimand (Homogeneity Assumption)

Homogeneity will be assessed for scientific question of interest part b, comparison amongst regimens. For this sensitivity estimator 1, the same included data, missing data assumption, and missing data handling rule (MANR) as well as the same approach to control the Type I error rate (Section 5.3.2.1) will be applied. The assumption for homogeneity of treatment effect across the stratification factor will be tested and, if heterogeneity is found statistically significant, a different statistical model will be used to define the sensitivity estimator.

# 5.3.2.2.1.1. Assumptions

- Missing Data for HBsAg are Missing Not at Random (MNAR)
- The treatment effect is non-homogeneous across strata

# 5.3.2.2.1.2. Analysis Methods

Homogeneity of treatment effect for each stratification factor separately will be tested using the weighted least squares chi-squared statistic (Lui K. J. et al., 2000) for one-way homogeneity. Tests of homogeneity will be assessed at the one-sided 10% level of significance.

Any heterogeneity found to be statistically significant will be explored using the following statistical model.

**Statistical model**: A logistic regression model on the primary efficacy endpoint using the randomization stratification factor and interaction terms. The model will include intervention arm, HBsAg level at screening (<100 IU/mL, 100 to <1,000 IU/mL or  $\geq$ 1,000 IU/mL), as factors, and the intervention arm-by-factor interaction terms.

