#### **VERSION HISTORY**

Document History	
Document	Date
Original SAP	20 September 2022
Amendment 1	23 August 2023
Amendment 2	10 June 2024

Amendment 2 (10 June 2024)

The main purpose of this SAP amendment is to document changes in the scope of the final analyses, based on results of the primary analysis.

Section number and Name	Description of Change	Brief Rationale
5.3.6. Comparisons Between Arm 1, 2 and Model-Based Virtual Nivolumab-Free JNJ- 3989+NA Regimen Control	Section Removed.	Virtual Control analysis is no longer of interest.
5.4.1.2. Continuous Endpoints	Section Updated.	Change from baseline value to the nadir is of interest only in HBsAg.
5.4.2.1.1. HBsAg Cut-offs and 5.4.2.1.4. HBeAg Cut- offs	Section Removed.	Cross-Tabulation for Quantitative Result vs. Qualitative Result Over Time for HBsAg and HBeAg removed as according to the protocol, qualitative HBsAg and HBeAg are only collected at screening and baseline.
5.4.2.2.1. HBsAg, HBeAg, HBV DNA and ALT	Section Updated.	
 
Waterfall plots of changes from Reference Timepoints in HBsAg removed
 
Descriptive statistics of changes from RTs in ALT removed
 
Changes from baseline analyses are removed for HBV DNA
 
Changes from baseline outputs are only displayed in the log 10 scale for all viral parameters
 
Change from Nivolumab RT and Follow-up Week 4 RT are of interest only for HBsAg
 

Section number and Name	Description of Change	Brief Rationale
5.5.1.3. and 5.5.2.3. Endpoints for Correlation	Section Removed.	Endpoints for Correlation is no longer of interest.
5.5.2.2.2. HBV RNA and HBcrAg	Section Removed.	Change from baseline value to the nadir is of interest only in HBsAg.
5.3.5. Subgroup Analyses of Primary Efficacy Endpoint and 5.7.6. Definition of Subgroups	Section Removed.	Subgroup Analysis is removed due to low number of observed events of interest.

## Amendment 1

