## 1.2. Study Design

This is a Phase 2, open-label, 2-arm, multicenter study to assess efficacy, safety, tolerability, PK and PD of a combination of JNJ-3989, nivolumab, and NAs in virologically suppressed, HBeAgnegative, chronic HBV-infected, adult participants.

Initially a target of approximately 44 virologically suppressed, HBeAg-negative chronic HBVinfected adult participants  $\geq 18$  (or the legal age of consent in the jurisdiction in which the study is taking place) to <56 years of age were planned to be enrolled in this study.

Due to the decision to not extend further enrollment beyond the planned enrollment period and proceed with a reduced sample size, the final sample size is 37 (18 in Arm 1 and 19 in Arm 2).

This open-label study will be conducted in 3 periods:

- Screening Period (6 weeks [if necessary, e.g. for operational reasons, can be extended to a maximum of 8 weeks decided on a case-by-case basis and in agreement with the Sponsor]).
- Study intervention (24 weeks):
  - Arm 1: JNJ-3989 Q1W for the first 4 weeks and then Q4W until Week 24 + nivolumab at Week 16 + NA QD
  - Arm 2: JNJ-3989 Q1W for the first 4 weeks and then Q4W until Week 24 + nivolumab Q4W at Weeks 16, 20, 24 + NA QD
- Follow-up (FU) Period (48 weeks), during which NA treatment will be continued.

The total duration of individual participation will be up to 72 weeks (screening not included). Participants will be considered to have completed the study if they have completed all the assessments of the end of study (EOS) visit (ie, FU Week 48).

A schematic overview of the trial is presented in Figure 1.

FU: follow-up; JNJ-3989: JNJ-73763989; n: number of participants; NA: nucleos(t)ide analog; Q1W: once weekly; Q4W: every 4 weeks; QD: once daily.

Note: In red: number of participants per arm according to the initial design. In blue: the actual sample size.

At baseline, participants who meet the eligibility criteria will be randomized in a 1:1 ratio to Arm 1 or Arm 2. Randomization will be stratified by absolute HBsAg level (<100 IU/mL, 100 to <1,000 IU/mL, and  $\geq$ 1,000 IU/mL) at screening, as assessed by quantitative HBsAg assay.

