# 2. STATISTICAL HYPOTHESES

The primary hypothesis of this study is that at least one of the combination regimens of JNJ-3989+nivolumab+NA is more efficacious than JNJ-3989+NA treatment, as measured by the primary efficacy endpoint (ie, the proportion of participants with HBsAg seroclearance at FU Week 24). Because the study does not include a regimen arm without nivolumab, the hypothesis is formulated assuming a fixed response rate for JNJ-3989+NA of 1% based on previous study 73763989HPB2001 (REEF-1).

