# 3. SAMPLE SIZE DETERMINATION

According to the initial protocol, a sample size of 20 participants per intervention arm which yielded  $\geq$ 85% statistical power to detect a  $\geq$ 15% and  $\geq$ 20% difference for the proportions of participants with HBsAg seroclearance at FU Week 24 in the 2 intervention arms, respectively, vs a fixed proportion of 1%. Statistical power to test the primary hypothesis was assessed for each of the intervention arms, using an exact test for a single proportion with a one-sided Type 1 error rate of 0.05 and applying the Hochberg procedure for multiple comparisons adjustment. The fixed rate assumed for the external active control (JNJ-3989 [200 mg]+NA treatment) is based on the data of study 73763989HPB2001 (REEF-1).

The total study sample size was adjusted to 44 participants (22 per arm) with 1:1 randomization ratio to each of the intervention arms, to account for an approximate 10% attrition rate.

Due to the decision to not extend further enrollment beyond the planned enrollment period and proceed with a reduced sample size, the final sample size is 37 (18 in Arm 1 and 19 in Arm 2). Under the same assumptions and methods of the initial protocol, an approximate sample size of 16 participants per intervention arm (assuming 10% attrition) yields  $\geq$ 75% statistical power to detect the same differences in HBsAg seroclearance at FU Week 24.

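### With 37 participants in three strata, the homogeneity test in Sensitivity Estimator 1 is often undefined, and its fallback model almost never has finite estimates when triggered

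*SAP*

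**What the plan says.** SAP 1.2 states: "Randomization will be stratified by absolute HBsAg level", in three categories (below 100, 100 to below 1,000, and 1,000 IU/mL or more). SAP 3 gives a final sample of 37, 18 in Arm 1 and 19 in Arm 2. The between-arm analysis of the primary endpoint is a stratified Mantel-Haenszel test (SAP 5.3.2.1.1.2) that assumes a homogeneous treatment effect across strata (SAP 5.3.2.1.3).

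Sensitivity Estimator 1 checks that assumption. SAP 5.3.2.2.1.2 says: "Homogeneity of treatment effect for each stratification factor separately will be tested using the weighted least squares chi-squared statistic", and "Tests of homogeneity will be assessed at the one-sided 10% level of significance". If the test is significant, the analysis moves to this model: "A logistic regression model on the primary efficacy endpoint using the randomization stratification factor and interaction terms". SAP 5.3.2.2.1 says a different model will then define the sensitivity estimator. Neither section has a zero-cell correction, an exact or penalised alternative, or a rule for when the test or the model cannot be computed.

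SAP Amendment 2 dropped the subgroup analyses of the primary endpoint, with this reason: "Subgroup Analysis is removed due to low number of observed events of interest". It left the homogeneity procedure in place.

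**The concern.** The weighted least squares statistic weights each stratum by the inverse of its estimated variance. A stratum with no responders in either arm has estimated variance zero, so the weight is infinite and the statistic does not exist. A stratum with no responders in only one arm has a variance estimate that is too small, which pushes the test towards rejection.

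The fallback has arm, a three-level stratum and their interaction: six parameters for six cells. Such a saturated model has finite maximum likelihood estimates only if every cell holds at least one responder and one non-responder. The empty cells that tend to make the test reject are the ones that break the model.

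At stake is the only planned check of the homogeneity assumption. Where the rule fails, the analyst must improvise after seeing the data.

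**Working it through.** **Inputs.** 18 and 19 participants (SAP 3). Three strata (SAP 1.2). Design rates 1% + 15 points = 16% and 1% + 20 points = 21% (SAP 2 and 3). Missing counts as non-response (SAP 5.3.2.1.4), so everyone in the full analysis set stays in a cell. Three strata give 2 degrees of freedom, and the upper 10% point of chi-squared is 4.605. *Assumptions:* all 37 were dosed; strata are either equal (6 v 6, 6 v 6, 6 v 7) or unequal (3 v 3, 6 v 7, 9 v 9); 5% in both arms serves as a low-response case.

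**The plan's own figures.** The SAP gives no operating characteristics for this test beyond its nominal level, but its power statement confirms the rates. The exact test against 1% rejects at two or more responders. At 16% and 21% this gives power 85.3% and 94.3% with 20 per arm, and 75.1% and 87.9% with 16 per arm, matching the stated figures of at least 85% and at least 75%.

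**Undefined test, by hand (equal strata, 16%/21%).** Chance of no responders in either arm of a stratum:
- 6 v 6: 0.84^6 × 0.79^6 = 0.3513 × 0.2431 = 0.0854
- 6 v 7: 0.84^6 × 0.79^7 = 0.3513 × 0.1920 = 0.0675

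At least one such stratum: 1 − (1 − 0.0854)² × (1 − 0.0675) = 0.220. Strata with 100% response in an arm add a negligible amount.

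**Finite fallback estimates, by hand (same case).** Chance that a cell has both outcomes:
- Arm 1, n = 6: 1 − 0.84^6 − 0.16^6 = 0.6487
- Arm 2, n = 6: 1 − 0.79^6 − 0.21^6 = 0.7568
- Arm 2, n = 7: 1 − 0.79^7 − 0.21^7 = 0.8079

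All six cells: 0.6487³ × 0.7568² × 0.8079 = 0.126.

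**Full enumeration.** For every outcome of the six cells, Q = Σ w_k(d_k − d̄)², where d_k is the stratum difference in proportions, w_k = 1/[p1(1−p1)/n1 + p2(1−p2)/n2] uses observed proportions, and d̄ is the weighted mean. The true difference is the same in every stratum, so each rejection is false.

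| Strata | Rates | Test undefined | Rejects when defined | Switch fires, all trials | Fallback finite, all trials | Fallback finite, if triggered |
|---|---|---|---|---|---|---|
| Equal | 16/21% | 22.0% | 16.7% | 13.0% | 12.6% | 1.4% |
| Unequal | 16/21% | 36.3% | 19.5% | 12.4% | 7.3% | 0.5% |
| Equal | 16/16% | 31.1% | 16.8% | 11.6% | 8.1% | 0.7% |
| Unequal | 16/16% | 44.8% | 19.4% | 10.7% | 4.7% | 0.3% |
| Equal | 5/5% | 89.7% | 12.9% | 1.3% | 0.04% | <0.01% |
| Unequal | 5/5% | 92.2% | 12.0% | 0.9% | 0.02% | <0.01% |

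**Effect of an unstated convention (equal strata, 16%/21%).** False rejection over all trials is 15.9% if zero-variance strata are dropped and the degrees of freedom reduced, 14.9% if 0.5 is added only in those strata, and 5.6% if 0.5 is added to every cell. Under all three, the fallback is finite in 1.2-1.5% of triggered trials.

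**The case against.** Four points can be made in the plan's favour.

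1. *False triggering is modest.* A reader might infer from the 17-20% that the switch fires by chance nearly twice as often as intended. That figure is conditional on the test being computable. An undefined test triggers nothing, and over all trials the switch fires in about 11-13% at 16%/16% and 16%/21% and about 1% at 5%/5%. This stands.
2. *Over-rejection depends on a convention.* Adding 0.5 to every cell makes the test conservative. The SAP defines the statistic by citing a paper on homogeneity of the risk difference, and whether that paper prescribes a correction cannot be checked from the documents. This stands: the inflation belongs to the statistic as the SAP describes it, without correction.
3. *Separation does not erase everything.* Fitted cell proportions and a likelihood-ratio interaction test remain finite, and the SAP speaks of exploring heterogeneity with the model. True, but the fitted proportions of a saturated model are the observed proportions, so the model then adds nothing to a table of counts.
4. *By-stratum summaries are already planned.* Protocol 9.4.2 promises efficacy summaries by stratification factor, and SAP 5.1.5 specifies Clopper-Pearson 90% intervals. This shows the fix is close at hand, but it does not remove the failing procedure. Amendment 2's removal of subgroup analyses also leaves it unclear whether those summaries survive.

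**Conclusion.** The concern holds as a minor to moderate defect. At the design rates the test cannot be computed in roughly a fifth to a third of trials, and when it triggers the fallback, all of the model's estimates are finite in about 0.5-1.4% of cases. At 5% response the test is undefined in about nine trials in ten. The documents give no event count, but the reason recorded in Amendment 2 makes a low-response case relevant.

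Two stronger readings are not supported. A reader might infer that the trial's main conclusion is at risk. It is not: the exact binomial tests against 1% do not use strata, and SAP 5.3.2.2.1 confines this estimator to the comparison between regimens, which is secondary. A reader might also infer that the interaction model can hardly ever be fitted. Without conditioning on the trigger, finite estimates occur in 7-13% of trials at the design rates; it is as a fallback that the model almost always fails.

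The percentages rest on assumed stratum splits. In the splits run here, unequal strata raise both the undefined and the non-finite rates.

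**What to change.** Delete the homogeneity test and the switch it triggers. Define Sensitivity Estimator 1 as responder counts by stratum and arm with Clopper-Pearson 90% intervals, plus stratum-specific differences in proportions with exact intervals, labelled descriptive. If a model is wanted, fit the interaction model by Firth-penalised likelihood, regardless of any test.

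Do not make Zelen's exact test the main check. It tests a common odds ratio, while SAP 5.3.2 summarises the effect as a difference in proportions. It also has little room to reject: with equal strata at the 10% level, no arrangement can reach significance in 33% of trials at 16%/21% and 98% at 5%/5%, given the margins.

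The cost is one SAP paragraph, no new data and standard software. There would be no formal homogeneity p-value. Amendment 2 states that it was based on results of the primary analysis, so this change must also be recorded as made after those results.

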# 5.3.2.2.2. Sensitivity Estimator 2 of the Main Estimand (Observed Case Analysis)

For this sensitivity estimator 2, the same statistical model, and data included will be used as for the main estimator (Section 5.3.2.1). The assumption for missing data and the rule to handle missing data have changed.

# 5.3.2.2.2.1. Assumptions

- Missing Data for HBsAg are Missing Completely at Random (MCAR) (Barnes A. et al., 2008)
- The treatment effect is homogeneous across strata

# 5.3.2.2.2.2. Missing Data Handling Rule

For sensitivity estimator 2, participants who withdrew from the study prior to Week 24 will not be included in the analysis. After taking into account all the intercurrent events and applying the intercurrent event strategies specified in Section 5.3.2, if a participant who did not experience any ICEs has missing response status for the primary endpoint then this participant will not be used for the analysis.

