## **D)** Intercurrent events:

- Treatment discontinuation prior to Week 24: if the participant discontinued treatment prior to Week 24 then s/he will be considered non-responder (composite strategy).
- Major protocol deviations affecting efficacy: Table 9 identifies the deviations considered intercurrent event. Participants with such deviations and who have missing data for the endpoint will be considered as non-responders (composite strategy). For all other deviations not considered intercurrent events, the data are used regardless of the occurrence of major protocol deviations (treatment policy strategy).

- Deaths prior to FU Week 24 are handled in a composite strategy as participants who die prior to FU Week 24 will be considered as non-responders.
- **E)** Population-level summary:
  - **a. Primary (comparison vs fixed external proportion):** Difference in proportion of participants with HBsAg seroclearance at FU Week 24 using a fixed external proportion of 1%.
  - **b.** Secondary (comparison amongst regimens): Difference in proportion of participants with HBsAg seroclearance at FU Week 24 between study intervention arms.

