# 5.3.2.2.3.2. Missing Data Handling Rule

For sensitivity estimator 3, participants who withdraw from the study prior to FU Week 24 will be considered as non-responders. After taking into account all the intercurrent events and applying the intercurrent event strategies specified in Section 5.3.2, if a participant who did not experience any ICEs has missing response status for the primary endpoint then the LOCF approach will be used as follows.

If the HBsAg value at FU Week 24 is missing, the LOCF in conjunction with the next available observation imputation approach will be used. The non-missing value closest to FU Week 24 will be selected among the non-missing values which are no earlier than 12 weeks prior to FU Week 24 or no later than 12 weeks after FU Week 24. If 2 non-missing laboratory values are equidistant, the later observation will be preferred. If a participant who did not experience any ICE and does not have HBsAg data within the analysis window of  $\pm 12$  weeks around FU Week 24 assessment will be considered as non-responder.

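### Sensitivity Estimator 2 excludes participants who leave the study before Week 24, although the estimand it serves, and the next sentence of the same rule, make them non-responders

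*SAP*

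**What the plan says.** SAP 5.3.2.2 plans sensitivity analyses by "constructing three sensitivity estimators for the main estimand as defined in Section 5.3.2". All three are therefore meant to serve the main estimand.

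Under part D of that estimand (SAP 5.3.2), treatment discontinuation is handled as follows: "if the participant discontinued treatment prior to Week 24 then s/he will be considered non-responder (composite strategy"). Death before FU Week 24 is also non-response. A protocol deviation flagged in Table 9 is non-response only when the endpoint is missing; SAP 5.3.2.1.4 confirms that an available FU Week 24 value is used.

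For the main estimator, SAP 5.3.2.1.4 adds: "Participants who withdraw from the study prior to FU Week 24 will be considered as non-responders". Estimator 3 (SAP 5.3.2.2.3.2) keeps that rule.

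Estimator 2 is the observed-case analysis. SAP 5.3.2.2.2 says "the same statistical model, and data included will be used as for the main estimator", then states that the missing-data assumption and handling rule differ. The assumption becomes missing completely at random (MCAR). The rule in SAP 5.3.2.2.2.2 has two sentences:

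- The first: "participants who withdrew from the study prior to Week 24 will not be included in the analysis".
- The second opens with "After taking into account all the intercurrent events and applying the intercurrent event strategies specified in Section 5.3.2, if a participant who did not experience". It thus leaves out only people free of intercurrent events whose response status is absent.

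**The concern.** The two sentences treat the same person differently. Take two participants who stop JNJ-3989 at Week 12. The one who stays in follow-up is a non-responder in Estimator 2. The one who leaves the study is excluded by the first sentence, yet the second sentence would keep that person as a non-responder. The SAP does not say which sentence prevails, so two programmers could produce different denominators.

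A sensitivity estimator should hold the estimand fixed and vary the missing-data assumption. Under a composite strategy the outcome of an early discontinuer is not missing, because it is defined as failure. MCAR can justify leaving out participants without an intercurrent event whose FU Week 24 HBsAg is absent. It gives no ground for removing participants already counted as failures. If they are removed, a gap between Estimator 2 and the main result mixes the MCAR handling with a change in how discontinuation is scored.

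**Working it through.** **Inputs.** Final sample 18 in Arm 1 and 19 in Arm 2; planning size 16 per arm after about 10% attrition (20 in the initial plan); target differences of 15 and 20 points over 1% (all SAP 3). Exact binomial test against 1%, one-sided 0.05, Hochberg over two arms (SAP 5.1.7), so the levels are 0.05 and 0.025. JNJ-3989 through Week 24 in both arms (SAP 1.2).

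**The plan's own figure.** At n = 16 and n = 20 the smallest rejecting count is 2 at both levels: P(X ≥ 2) under 1% is 0.0109 and 0.0169, while P(X ≥ 1) is 0.149 and 0.182. Power is P(X ≥ 2) at 16% and 21%:

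- n = 20: 85.3% and 94.3%, against a stated 85% or more.
- n = 16: 75.1% and 87.9%, against a stated 75% or more.

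Both stated powers reproduce.

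**Does leaving before Week 24 imply the intercurrent event?** The last scheduled JNJ-3989 dose is at Week 24 in both arms. A participant who leaves earlier has not completed treatment, so has discontinued before Week 24 and is a non-responder under SAP 5.3.2.

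**Treatment of that participant, rule by rule.**

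| Rule | Withdrawal before Week 24 |
|---|---|
| Main estimator, 5.3.2.1.4 | Non-responder |
| Estimator 2, first sentence of 5.3.2.2.2.2 | Excluded |
| Estimator 2, second sentence of 5.3.2.2.2.2 | Non-responder, through the 5.3.2 strategy |
| Estimator 3, 5.3.2.2.3.2 | Non-responder |

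**Size per arm.** With x responders, n in the arm and w withdrawals before Week 24, the estimand gives x/n and the first sentence gives x/(n-w). The shift is x/(n-w) - x/n: zero if x = 0 or w = 0, positive otherwise. Neither x nor w is in the documents, so the ranges here are assumptions; w = 2 is roughly the planned attrition. For example, 2/18 = 11.1% becomes 2/16 = 12.5%, and 3/19 = 15.8% becomes 3/17 = 17.6%. Shift in percentage points, Arm 1 / Arm 2:

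| x | w = 1 | w = 2 | w = 3 | w = 4 |
|---|---|---|---|---|
| 1 | 0.3 / 0.3 | 0.7 / 0.6 | 1.1 / 1.0 | 1.6 / 1.4 |
| 2 | 0.7 / 0.6 | 1.4 / 1.2 | 2.2 / 2.0 | 3.2 / 2.8 |
| 3 | 1.0 / 0.9 | 2.1 / 1.9 | 3.3 / 3.0 | 4.8 / 4.2 |
| 4 | 1.3 / 1.2 | 2.8 / 2.5 | 4.4 / 3.9 | 6.3 / 5.6 |

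**Effect on the test against 1%.** In Arm 1, two responders give p = 0.0138 with n = 18 and p = 0.0109 with n = 16; both are below 0.025. One responder gives 0.166 and 0.149; neither rejects. A single responder would reject only if the denominator fell to 5 (1 - 0.99^5 = 0.049) at level 0.05, or to 2 (1 - 0.99^2 = 0.020) at level 0.025. The threshold stays at two responders throughout the range.

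**Effect on Arm 1 minus Arm 2.** Crude differences, ignoring strata, with an assumed 3/18 and 4/19:

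- No exclusions: 16.7% - 21.1% = -4.4 points.
- Two excluded from Arm 1 only: 3/16 - 4/19 = -2.3 points.
- Two excluded from Arm 2 only: 3/18 - 4/17 = -6.9 points.

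The shift can go either way.

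**The case against.** The best defence is that the SAP files study withdrawal under missing data. Part D of SAP 5.3.2 lists treatment discontinuation, selected deviations and death, but not withdrawal. Withdrawal appears in the missing-data rules, and the disposition tables in SAP 5.2 count stopping study intervention separately from leaving the study. SAP 5.3.2.2.2 also declares openly that the missing-data rule changes. On this reading, an observed-case analysis that drops withdrawals does what its label says.

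The filing is as described, and the change of rule is declared. Neither resolves the conflict. A withdrawal before Week 24 is also a treatment discontinuation before Week 24, and the second sentence of the rule says the strategy for that event still applies. The defence does work for withdrawals between Week 24 and FU Week 24 with no intercurrent event: leaving them out is a proper MCAR analysis.

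It may also be said that Week 24 is a slip for FU Week 24, the time point used for the main estimator and Estimator 3. Correcting it would not help, because withdrawals before Week 24 would still be excluded.

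Three further objections stand. A programmer could follow the second sentence, in which case nothing is wrongly removed. The exclusion is a visible change of denominator that the disposition tables and listings in SAP 5.2 allow a reader to trace. And the shift may be small: SAP Amendment 2 cites a low number of observed events when it removes the subgroup analyses.

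**Conclusion.** The contradiction is in the text and should be corrected. Followed literally, the first sentence raises an arm's proportion whenever that arm has at least one responder and one withdrawal before Week 24, by about 0.3 to 6.3 points for the assumed 1 to 4 of each. The implication from withdrawal to discontinuation rests on the JNJ-3989 schedule running to Week 24.

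A reader might infer more than this, and the documents do not support it:

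- That Estimator 2 is biased upward in general. This holds per arm under the condition above; for the between-arm comparison the direction depends on which arm loses participants.
- That the exclusion could produce a positive test. The two-responder threshold does not move in the range examined.
- That Estimator 2 certainly removed known failures or cannot be interpreted. The text is ambiguous rather than settled, and the change can be traced.

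This is a minor point about one sensitivity analysis; the main estimator is unaffected.

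**What to change.** Delete the first sentence of the rule in SAP 5.3.2.2.2.2 and let the second govern. The SAP 5.3.2 strategies then apply as written:

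- Treatment discontinuation before Week 24, including through study withdrawal, is non-response.
- Death before FU Week 24 is non-response.
- A flagged protocol deviation is non-response only if the endpoint is missing.
- Only participants without an intercurrent event and with missing FU Week 24 HBsAg are left out, including such withdrawals between Week 24 and FU Week 24.

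A broader rewording that makes every intercurrent event before Week 24 a failure should be avoided. It would override observed FU Week 24 values in participants with flagged deviations, such as a missed or out-of-window dose in Table 9, and would not cover deaths between Week 24 and FU Week 24. If the exclusion is really wanted, relabel the analysis as a supplementary estimand.

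The text change is one sentence, plus a rerun of this estimator if it was programmed from the first sentence. SAP Amendment 2 (10 June 2024) was written with the primary results in hand, so the report should state how Estimator 2 was run, give the number of withdrawals before Week 24 by arm, and label the corrected version as a post-results correction.
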